### ECG Summaries

The following analyses will be performed for each applicable ECG parameters (RR, PR, QRS, QT, ventricular rate -denoted as HR in what follows-, and QTc) by treatment group, during the on-treatment period. The denominator to calculate percentages for each category is the number of patients evaluable for the category.

- Pearson correlation between QT and RR, QTc (QTcB, QTcF and, if applicable, QTcP) and HR using individual (non-averaged) baseline assessments.
- For each of the ECG parameters (HR, and QT, QTc, QRS, PR intervals), descriptive statistics at baseline, at each post-baseline time point and changes from baseline at each post-baseline time point.
- Frequency (number and percentage) of patients with notable ECG values according to the following categories:
  - QT/QTc increase from baseline >30 ms, >60 ms.

- $QT/QTc > 450 \text{ ms}, > 480 \text{ ms}, > 500 \text{ ms}.$
- $HR \leq 50 \text{ bpm}$  and decrease from baseline  $\geq 20 \text{ bpm}.$
- $HR \geq 120 \text{ bpm}$  and increase from baseline  $\geq 20 \text{ bpm}.$
- $PR \geq 220 \text{ ms}$  and increase from baseline  $\geq 20 \text{ ms}.$
- $QRS \geq 120 \text{ ms}.$

Frequency (number and percentage) of patients with post-baseline qualitative ECG abnormalities (morphology) will be summarized.

Patients with notable ECG interval values and qualitative ECG abnormalities will be listed for each patient and time point and the corresponding notable values and abnormality findings will be included in the listings.

Unscheduled ECG measurements will not be used in computing the descriptive statistics for change from baseline at each post-baseline time point. However, they will be used in the analysis of notable ECG changes and the shift table analysis of notable QT parameters.

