9. **Triplicate 12 Lead ECG:** See [Section 7.1.5](#) for details. At each time point, 3 consecutive 12 lead ECGs will be performed approximately 2 minutes apart to determine mean QTc. When coinciding with blood sample draws for PK, ECG assessment should be performed prior to blood sample collection, such that the blood sample is collected at the nominal time. ECGs will be collected as follows: a) at Screening; b) On Cycles 1-8/Day 1, at pre PF-05082566 infusion and end of MK-3475 infusion; and c) at End of Treatment. If the mean QTc interval is prolonged (>500 msec), then the ECGs should be reevaluated by a qualified person at the center for confirmation. Additional triplicate ECGs may be performed as clinically indicated. While pre-dose ECG assessments will be required for all patients, post-dose ECG assessments will be required only for patients in dose escalation cohorts.
10. **Hematology:** No need to repeat on C1D1 if baseline assessment performed within 7 days prior to that date. To be performed weekly. If during the first 2 cycles of treatment a grade 4 hematologic event is evident, the hematology assessment should be repeated at least every other day to assess for events qualifying as DLT. See [Table 4](#) for the Required Laboratory Tests list.
11. **Blood Chemistry:** No need to repeat on C1D1 if baseline assessment performed within 7 days prior to that date. To be performed weekly. See [Table 4](#) for Laboratory Tests list.
12. **Coagulation:** No need to repeat on C1D1 if baseline assessment performed within 7 days prior to that date. To be performed weekly for Cycle 1 and on Day 1 for all remaining cycles and at the End of Treatment visit. See [Table 4](#) for Laboratory Tests list.
13. **Urinalysis:** During the treatment period to be performed when clinically indicated. If protein $\geq 2+$ by semiquantitative method (eg, urine dipstick), protein will be quantified by 24 hour urine collection (see [Table 4](#)). Urine reflex microscopy is required whenever urine multitest dipstick is positive for blood or protein.

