7.1.5. ECG Assessments

Electrocardiogram (ECG): Triplicate 12-lead (with a 10-second rhythm strip) tracing in the supine or semi-recumbent position will be used for all ECGs. It is preferable that the machine used has a capacity to calculate the standard intervals automatically. At each time point, three consecutive 12 lead ECGs will be performed approximately 2 minutes apart to determine mean QTc. When coinciding with blood sample draws for PK, ECG assessment should be performed prior to blood sample collection, such that the blood sample is collected at the nominal time. If the mean QTc interval is prolonged (>500 msec), then the ECGs should be re-evaluated by a qualified person at the center for confirmation. Clinically significant abnormal findings in baseline ECGs will be recorded as medical history. Clinically significant findings seen on the follow-up ECGs should be recorded as adverse events. ECG assessments beyond Screening will not be required for patients in dose expansion cohorts (see the [Schedule Of Activities](#)). Additional ECGs may be performed as clinically indicated. While pre-dose ECG assessments will be required for all patients, post-dose ECG assessments will be required only for patients in dose escalation cohorts.

Prior to concluding that an episode of prolongation of the QTcF interval is due to study drug, thorough consideration should be given to potential precipitating factors (eg, change in patient clinical condition, effect of concurrent medication, electrolyte disturbance) and possible evaluation by specialist.

If patient experiences a cardiac or neurologic AE (specifically syncope, dizziness, seizures, or stroke), an ECG (triplicate) should be obtained at the time of the event.

When matched with PK sampling, the ECG must be carried out before each PK sample drawing such that the PK sample is collected at the nominal time (ie, the timing of the PK collections over rides the timing of the ECG collections).

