9.6.3. ECG

The analysis of ECG results will be based on safety analysis set patients with baseline and on-treatment ECG data. The most recent ECG collected prior to the first day of dosing will be considered the baseline ECG. ECG measurements (an average of the triplicate measurements) will be used for the statistical analysis and all data presentations. Any data obtained from ECGs repeated for safety reasons after the nominal time-points will not be averaged along with the preceding triplicates. Interval measurements from repeated ECGs will be included in the outlier analysis as individual values obtained at unscheduled time points.

QT intervals will be corrected for heart rate (QTc) using standard correction factors [ie, Fridericia's (default correction), Bazett's, and possibly a study specific factor, as appropriate]. Data will be summarized and listed for QT, HR, response rate (RR), PR, QRS, QTcF (and other correction factors, eg, QTcB as appropriate) by dose. Individual QT (all evaluated corrections) intervals will be listed by time and dose. The most appropriate correction factor will be selected and used for the following analyses of central tendency and outliers and used for the study conclusions. Descriptive statistics (n, mean, median, standard deviation, minimum, and maximum) will be used to summarize the absolute corrected QT value and changes from baseline in corrected QT after treatment, by dose and time point. For each patient and by treatment, the maximum change from baseline will be calculated as well as the maximum post-baseline value across time-points. Categorical analysis will be conducted for the maximum change from baseline in corrected QT and the maximum post-baseline QT value.

The effect of drug concentrations on corrected QT change from baseline will be explored graphically. Additional concentration-corrected QT analyses may be performed. Data may be pooled with other study results and/or explored further with PK/PD models.

Shift tables will be provided for baseline vs. worst on study QTc (one or more correction method will be used) using Maximum CTCAE Grade. As well as tables of ECG abnormality at baseline (yes, no, not done: (n, %)). Patients experiencing clinically-relevant morphological ECG changes will be summarized (including frequency and percentage).

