## 5.2. General Methods

As described in [Section 3.4](#), in this study ‘**treatment group**’ refers to one of the following:

- Cohort -1: PF-05082566 0.2 mg/kg q3wks + MK-3475 2mg/kg q3wks;
- Cohort 1: PF-05082566 0.45 mg/kg q3wks + MK-3475 2mg/kg q3wks;
- Cohort 2: PF-05082566 0.9 mg/kg q3wks + MK-3475 2mg/kg q3wks;
- Cohort 3: PF-05082566 1.8 mg/kg q3wks + MK-3475 2mg/kg q3wks;
- Cohort 4: PF-05082566 3.6 mg/kg q3wks + MK-3475 2mg/kg q3wks;
- Cohort 5: PF-05082566 5 mg/kg q3wks + MK-3475 2mg/kg q3wks.

Baseline characteristics, disposition and efficacy data will be summarized based on the FAS by treatment group.

DLTs will be summarized based on the DLT-evaluable set by treatment group.

Other safety data, exposure data, concomitant medications and non-drug treatments will be summarized based on the safety analysis set by treatment group.

PK data will be summarized based on the PK analysis set by treatment group.

Biomarker data will be summarized based on the biomarker analysis set by treatment group.

Immunogenicity data will be summarized based on the immunogenicity analysis set by treatment group.

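### QTc outlier and shift tables split by dose alone mix patients with different ECG ascertainment in the expansion-dose row, and the protocol contradicts itself on which ECGs expansion patients have

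*SAP*

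**What the plan says.** **Which ECGs are scheduled.** Footnote 9 of the Schedule of Activities sets ECGs at Screening and then: "On Cycles 1-8/Day 1, at pre PF-05082566 infusion and end of MK-3475 infusion; and c) at End of Treatment". It adds: "While pre-dose ECG assessments will be required for all patients, post-dose ECG assessments will be required only for patients in dose escalation cohorts". Protocol 7.1.5 contains the same sentence, but the same paragraph also says: "ECG assessments beyond Screening will not be required for patients in dose expansion cohorts".

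**How outliers are counted.** Protocol 9.6.3 says that for each patient "the maximum change from baseline will be calculated as well as the maximum post-baseline value across time-points", followed by a categorical analysis of both and a shift table of baseline against worst on-study QTc. SAP 6.6.7 counts patients with an increase above 30 or 60 ms, or a value above 450, 480 or 500 ms. Unscheduled ECGs count here and in the shift table, though not in the by-time-point statistics.

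**How the tables are grouped.** The ECG analyses are produced "by treatment group, during the on-treatment period". SAP 3.4.1 and 5.2 define treatment group as one of six dose levels, and 5.2 says: "Other safety data, exposure data, concomitant medications and non-drug treatments will be summarized based on the safety analysis set by treatment group". SAP 6.4 plans no subset analyses. On denominators, SAP 6.6.7 says: "The denominator to calculate percentages for each category is the number of patients evaluable for the category". The SAP does not define evaluable for this purpose; the protocol's ECG set (9.1) asks for a baseline and at least one on-study measurement.

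**Who shares a row.** The expansion dose is the estimated MTD or a lower dose (protocol 3.5), so it will normally be a dose at which escalation patients were also treated.

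**The concern.** A count of patients with at least one notable value depends on how many ECGs each patient has and when they are taken. Twice as many ECGs give more chances of crossing a threshold by noise alone, and an end-of-infusion ECG can show an effect that a pre-dose ECG three weeks later may not. The plan puts patients with different ECG schedules in one row and counts each equally in the denominator.

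At stake is how the categorical QTc tables are read across doses. A difference between the expansion dose and the other doses could come from the ECG schedule rather than the drug. Because the protocol gives two incompatible rules for expansion patients, a reader of the table could not tell which way the distortion runs.

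**Working it through.** The documents give no expected QTc outlier rate and no QTc variability, so there is no planned figure to reproduce. The check has three parts.

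**1. Scheduled post-baseline time points (footnote 9).** Cycle 1 pre-dose is taken as baseline, following SAP 3.4.1. End of Treatment, about 28 days after the last dose, falls inside the 30-day on-treatment window unless new anti-cancer drug therapy starts first. For a patient who receives C cycles (C up to 8):

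- Pre-dose after baseline: C − 1. End of Treatment: 1. Post-dose: C.
- Escalation: (C − 1) + 1 + C = 2C.
- Expansion, if pre-dose ECGs apply to all: (C − 1) + 1 = C.
- Expansion, if the Screening-only sentence applies: 0.

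Over eight cycles this is 16 against 8 (or 0). Over three cycles it is 6 against 3 (or 0).

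**2. Effect on the count under the pre-dose-for-all reading.** Assumptions not in the documents: baseline and later triplicate means are independent normal with within-patient SD *s*, and there is no drug effect. With *n* post-baseline time points, baseline error e₀ ~ N(0, s²) and threshold *t*,

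P(max change > t) = 1 − E[ Φ((t + e₀)/s)ⁿ ].

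| Threshold | SD (ms) | Cycles | Escalation | Expansion |
|---|---|---|---|---|
| >30 ms | 8 | 8 | 4.2% | 2.5% |
| >30 ms | 10 | 8 | 13.9% | 9.0% |
| >30 ms | 12 | 8 | 25.7% | 17.8% |
| >30 ms | 10 | 3 | 7.4% | 4.4% |
| >60 ms | 10 | 8 | 0.017% | 0.009% |
| >60 ms | 12 | 8 | 0.28% | 0.15% |

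The table would show a pooled row. Take 9 escalation patients (the stopping rule in protocol 3.2) and an assumed 10, 20 or 40 expansion patients, since the protocol gives no expansion size. At SD 10 ms over eight cycles:

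- 10 expansion: (9 × 13.9 + 10 × 9.0)/19 = 11.3%
- 20 expansion: (9 × 13.9 + 20 × 9.0)/29 = 10.5%
- 40 expansion: (9 × 13.9 + 40 × 9.0)/49 = 9.9%

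A dose with escalation patients only would show 13.9% for the same true QTc.

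As a sensitivity case, suppose a true effect of 10 ms at end of infusion and none pre-dose. At SD 10 ms over eight cycles the rates are 32.2% against 9.0%, and the pooled row shows 20.0%, 16.2% or 13.3%.

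The absolute-value categories (>450, >480, >500 ms) also depend on the baseline distribution and were not quantified.

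**3. The Screening-only reading.** Expansion patients then have no scheduled post-baseline ECG, and most would not be evaluable. Those who enter do so mainly through clinically indicated ECGs, including those that 7.1.5 calls for after certain cardiac or neurologic events. SAP 6.6.7 counts these as notable values when they qualify. The row then adds patients selected because something prompted an ECG, which could push the rate up.

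**The case against.** **The direction is not fixed.** A reader might infer that the expansion dose must look cleaner than the others by construction. The documents do not support that. It follows only if pre-dose ECGs apply to all patients, and then only in expectation; under the Screening-only sentence the rate could go up. This objection stands. What survives is that the row mixes unequal ascertainment under either reading.

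**A peak effect is not lost.** A reader might also infer that an end-of-infusion effect would disappear from the results. It would not. SAP 6.6.7 gives change from baseline at each post-baseline time point, where post-dose rows can contain only patients with post-dose ECGs, and it lists notable values by patient and time point. Protocol 9.6.3 adds a graphical look at concentration against QTc change. The problem is confined to the categorical outlier and shift tables.

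**Post-dose ECGs do not stop when the study enters expansion.** The rule follows the patient's cohort. Escalation patients keep post-dose ECGs through Cycle 8, including those at the expansion dose.

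**The size is modest.** The 16-against-8 contrast needs eight cycles of treatment, the SDs are assumed, and >30 ms is the change category most sensitive to noise. All of this stands, and pooling with escalation patients narrows the gap further.

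**Nothing formal depends on it.** No hypothesis test is planned and no between-dose QTc comparison is specified. The RP2D rests mainly on DLTs and feasibility and need not be the expansion dose. The denominator sentence is also ordinary in itself, and the explicit maximum rule is in the protocol rather than the SAP. These points limit the weight of the concern. They do not make the pooled row interpretable, because counting a patient with any qualifying on-treatment value works in the same way as taking the maximum.

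**Conclusion.** The concern holds in a limited form. The ECG passages in footnote 9 and protocol 7.1.5 contradict each other and must be reconciled. Whichever applies, the notable-value, maximum-change and worst-grade shift tables by dose alone combine patients with different ECG ascertainment at the expansion dose.

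Under the pre-dose-for-all reading, the expected >30 ms rate there is about 10-11% in a pooled row, against 13.9% at an escalation-only dose with the same true QTc. This rests on an SD of 10 ms, independent errors, no drug effect, eight cycles, and 9 escalation plus 10-40 expansion patients. The difference for >60 ms is negligible under the same no-effect model. Under the Screening-only reading the rate could be pushed up by an amount the documents do not allow one to estimate.

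This is a cheap improvement to a descriptive table. It does not show that the trial's QTc assessment as a whole is biased.

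**What to change.** 1. Reconcile footnote 9 with the two conflicting sentences in protocol 7.1.5, so that the ECG schedule for expansion patients is stated once.
2. In SAP 6.6.7, show the notable-value, maximum-change and shift tables separately for escalation and expansion patients within each dose level.
3. Make any between-dose reading of outlier rates only on scheduled time points common to both phases. With pre-dose ECGs for all, these are the pre-dose and End of Treatment ECGs, 8 against 8 over eight cycles; at SD 10 ms with no drug effect the >30 ms rate is then 9.0% in both phases. If no common on-treatment time points remain after step 1, say so and do not compare expansion patients with other doses on these tables.
4. For post-dose categories, use only patients with a post-dose ECG as the denominator.

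The cost is SAP wording, extra table rows and smaller cells, so percentages within each phase will be less stable. No additional ECGs are needed.

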#### **6.6.8. Physical Examination**

Number and percentage of patients with abnormal findings in physical examination will be summarized by body system.

#### **6.6.9. ECOG Performance Status**

The ECOG shift from baseline to highest score during the on-treatment period will be summarized by treatment group. ECOG performance status with shift from ECOG=0 or 1 to ECOG 2 or higher will also be presented in a data listing.

### **7. INTERIM ANALYSES**

There is no formal interim analysis planned for this study. A Dose Escalation Steering Committee (DESC) was established to review safety data. Periodical DESC meetings will be scheduled to make decisions on escalation and de-escalation following the TITE-CRM design.

#### **7.1. Introduction**

Not Applicable.

#### **7.2. Interim Analyses and Summaries**

Not Applicable.

